## **2.4.2 Minimization of Bias**

There will be no specific gender or ethnic background for enrollment.

## **2.4.3 Pre-Study Period**

## **2.4.4 Study Period**

### **Methods:**

## **2.4.6 Observations and Measurements**

### **2.4.6.3 Primary Outcome Measures**

Primary outcomes:

1. Patient adherence and determination of feasibility and acceptance with the virtual clinic and telehealth visits based on the FIM® (feasibility of intervention measure), IAM® (intervention appropriateness measure) and the AIM® (acceptance of intervention measure)
2. Patient attendance record
3. Number of on-time arrivals to the virtual visit
4. Number of patient successfully completed online questionnaires after initial training.
5. Patient primary care or clinic physician feedback using the tools in #1 and open ended comments.

### **2.4.6.4 Secondary Outcome Measures**

[figure not shown]
Secondary outcomes: (to compare patient characteristics to historical non-COVID-19 patients with PICS)

1. ICU Memory Tool® (measures recall and aids in our understanding of the quality of life)
2. PROMIS®29 Profile (measures anxiety, depression, fatigue, pain, physical function, sleep and ability to participate in social roles),
3. MOCA-5 minute® (measures cognitive function),
4. Katz and Lawton® (measures activities of daily living),
5. PG-SGA short form® (screens for malnutrition risk),
6. Five-time sit-to-stand, and Two-minute step test.

### **2.4.6.5 Statistical Methods**

Descriptive statistics will be used to summarize the data. Continuous variables will be reported as medians and interquartile ranges or means and standard deviations as appropriate. Categorical variables will be reported as frequencies and percentages. Changes in the scores or times of the ICU Memory Tool®, PROMIS®29 Profile, MOCA-5 minute, Katz and Lawton®, PG-SGA short form®, Five time sit-to-stand and Two-minute step test, from hospital discharge to 3- and 6-month post discharge will be estimated using the Wilcoxon Signed Rank Test (non-parametric alternative to t-test) and compared across different categorical variables (e.g. age, gender, discharged directly to

CONFIDENTIAL: This document is the intellectual property of [name]. Acceptance of this document constitutes the agreement by the recipient that no unpublished information contained herein will be published or disclosed without prior written approval.

home, 30-day readmission) using ANOVA and continuous variables (e.g. APACHE IV, ICU length of stay) using ANCOVA.

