Although individual symptoms of PICS have been reported over the past decade, PICS first became recognized in 2015. Often signs and symptoms of PICS do not manifest until the patient has returned home, requiring evaluation and treatment in the outpatient setting. A wide variety of follow-up strategies to prevent/limit the impairments associated with PICS for ICU survivors have been examined which include: communication of care between the ICU team and primary provider, peer support groups, follow-up phone-calls from the ICU staff to patient, and scheduled in-person consultations. There has also been the establishment of PICS outpatient clinics to attempt to manage this complex patient population. The goals of these clinics have been to improve recovery, decrease the cost burden on the healthcare system and improve the patient's quality of life. Unfortunately, very few outpatient PICS clinics currently exists and those that do are generally in metropolitan areas. However, according to the American Hospital Association approximately 80% of ICU beds are located in community hospitals, suggesting these clinic may not be easily accessible by the majority of patients who need them (<https://www.aha.org/statistics/fast-facts-us-hospitals>).

Services offered and clinical professionals available may vary from clinic to clinic. Most have a medical director specializing in PICS and nursing support. Other professionals may include some combination of a neuropsychologist, social worker, pharmacist, physical therapy, occupational therapy, case manager and dietitian. In clinics with limited professionals, services include the patient evaluation and then coordination of care with referrals to primary care, subspecialty services,

CONFIDENTIAL: This document is the intellectual property of [name]. Acceptance of this document constitutes the agreement by the recipient that no unpublished information contained herein will be published or disclosed without prior written approval.

physical and occupational therapy as needed. A review of 30 clinics demonstrated the majority were limited to physician and nurse interactions while incorporating patient self-evaluation tools. Most patients returned for their first clinic visit within six to twelve weeks after hospital discharge, although some initiated visits within 3 weeks.

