### **2.4.1 Study Procedures**

[figure not shown]
Study Procedures – Patient and PCP involvement	
Consent	Verbal consent is being sought. RC will be in a private space and obtain consent. All visits with the patient will be “virtual”.
Chart Review	Once patient consent is obtained, a prospective or retrospective chart review (depending on availability of research team members) will be conducted to obtain several data points (see attached).
Day 1	RC: Add patient to enrollment log: Study ID, first name, 3 letters of last name, MRN#, hospital discharge date, date returned home (if different from discharge date), and patient preferred email and phone number. If patient consents, PCP name, office phone number and fax number. This will be in a password protected Excel file available only to research team members.
Day 1	RC: Document date/time of consent, upload pdf of note to RedCap

CONFIDENTIAL: This document is the intellectual property of [name]. Acceptance of this document constitutes the agreement by the recipient that no unpublished information contained herein will be published or disclosed without prior written approval.

[figure not shown]
Day 1	
RC: Patient emailed a copy of the verbal consent, as well as, an information sheet, including a timeline for the study and “what to expect” and “what not to expect”.
 
What to expect: Timeline for study, Initial surveys, follow up surveys at 3 and 6 months, team visits (when – at minimum every 12 weeks; time commitment – 60-75 minutes), bi-weekly touch base email by RCs, individual visits with team members if warranted, summary of team recommendations after each visit, potential contact from PCP (if patient consented for information to be shared) and contact information for RC and PI for any questions or concerns throughout the study period. All providers engaging in telehealth visits will be licensed in the state where the participant lives.
 
What not to expect: Clinic physicians or other providers to write prescriptions, order lab tests or perform any treatments

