Day 1-2  Week 10 post initial visit And Week 22 post initial visit	
RC: If patient not enrolled in MyChart or has forgotten how to access, call patient and walk them through obtaining access. Direct link (attached to the patient’s study ID) will be emailed or texted (per patient preference) to access the following surveys, requesting one week turn-around time:
 
ICU Memory Tool® (measures recall and aids in our understanding of quality of life)
 
PROMIS®29 Profile (measures anxiety, depression, fatigue, pain, physical function, sleep and ability to participate in social roles)
 
MOCA-5 minute® (measures cognitive function)
 
PG-SGA short form® (screens for malnutrition risk)

Day 2-9  Week 11 and Week 23 post initial visit	
RC: Will send form email from PI to PCP (if patient agreed to share information) providing an overview of the study (see attached)
 
RC will obtain notice from RedCap when surveys opened. RC will check completeness of survey responses. If surveys not completed within 5 days, send reminder email. If not completed in 7 days, call patient offering to administer surveys over the phone.

Day 11  Week 11 and Week 23 post initial visit	
RC: If patient does not complete surveys within 7 days of receipt and has not responded to phone calls; considered an enrollment fail (start of study) or withdrawal from study (repeat surveys), document on enrollment log.

Day 2-11  Week 11 and Week 23 post initial visit	
RC: If surveys completed, send thank you email. Email and/or call patient to schedule first virtual visit. Email link to research team members for them to review responses in RedCap.

Day 9 – 18  Week 12 and Week 24 post initial visit	
RC: Schedule initial 60-75 minute virtual assessment based on MD schedule. Email all team members to obtain availability in non-physician visit time. Send outlook calendar appointments to team members. All providers engaging in telehealth visits will be licensed in the state where the participant lives.

1-2 days before virtual team visit	
RC: Send reminder email to research team members who will be on the visit. Send agenda for call – member/time slot. Send instructions/link for team members to join the virtual visit. Email the patient the instructions on how to access the virtual appointment in MyChart or the HIPPA approved WashU ZOOM link.

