CONFIDENTIAL: This document is the intellectual property of [name]. Acceptance of this document constitutes the agreement by the recipient that no unpublished information contained herein will be published or disclosed without prior written approval.

30 min before each virtual team visit	RC: Email/call patient to address any concerns/questions regarding accessing virtual visit. RC will be “host” of the link for the visit.
Time of virtual team visit	RC: Send text to research team that patient has successfully entered the virtual visit.
During virtual team Visit	RC will function as timekeeper – send “chats or texts” to research team members to keep them on time. Team members will speak one at a time, with other members on mute. MD will start with introduction and overview that summary of recommendations after the visit will be sent to the patient’s PCP and the patient, emphasizing the patient and the PCP will be responsible for implementing and monitoring recommended treatments. Each professional will follow with introduction/any additional questions. The physical therapist and occupational therapist will go last to complete the following if the patient agrees/is able: Katz and Lawton® (measures activities of daily living) Five time sit-to-stand Two minute step test All providers engaging in telehealth visits will be licensed in the state where the participant lives.
1-3 days post virtual team visit	Team Members: responsible for documenting in EPIC their note/summary within 2 days of visit RC: Email patient summary of recommendations are available in MyChart for patient to access. Email PCP that summary is available in MyChart, or fax summary if PCP does not have access to MyChart. Clinic MD may choose to contact PCP personally regarding patient evaluation if they deem necessary.
2, 4, 6, 8, 10 weeks post initial and second virtual team visit	RC: Phone call to patient – What recommendations have been implemented? Any questions for any member of the research team? Any team member: may touch-base with the patient or treating professional (home physical therapist) if recommendations have been implemented by the PCP (e.g. physical therapy, change in medication, change in diet) to determine if they have any questions regarding the treatment initiated. If team member desires a virtual visit with patient – RC will host.

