#### **2.4.6.6 Sample Size**

A consensus sample would be optimal in this feasibility study (all patients meeting criteria consented and participated), however since that is unlikely, a convenience sample will be used. The future of patients with COVID-19 disease requiring ICU admission is uncertain. A conservative estimate of 50% of these patients will develop PICS. In the first month at BJH, 29 patients were discharged from the ICU. This translates into approximately 15 patients per month. Although this number may increase or decrease due to uncertainties surrounding the disease. Previous studies (see literature review) suggest care for PICS should begin within 12 weeks of discharge. Therefore once IRB approval is obtained, patients discharged within the past 10 weeks will be screened for possible participation. A post-hoc power analysis will be done.

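### Change is to be analysed from hospital discharge to 3 and 6 months after it, but no instrument is scheduled at discharge and the repeats are counted from the first virtual visit

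*Combined protocol and SAP*

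**What the plan says.** The Statistical Methodology entry of the Synopsis and section 2.4.6.5 use the same sentence: changes in the ICU Memory Tool, PROMIS-29, MoCA 5-minute, Katz and Lawton, PG-SGA short form, sit-to-stand and step test "from hospital discharge to 3- and 6-month post discharge will be estimated using the Wilcoxon Signed Rank Test". The changes are then compared across patient characteristics by ANOVA and ANCOVA.

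The table in 2.4.1 sets a different clock:

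- Day 1 is the day of enrolment and consent. Under 3.3, consent follows a telephone screen for possible PICS symptoms.
- The four surveys (ICU Memory Tool, PROMIS-29, MoCA 5-minute, PG-SGA) are sent on Day 1-2 and again at "Week 10 post initial visit And Week 22 post initial visit".
- The virtual team visits take place on Day 9-18 and at "Week 12 and Week 24 post initial visit".
- Katz and Lawton, sit-to-stand and the step test are done only within those visits: "The physical therapist and occupational therapist will go last to complete the following if the patient agrees/is able".

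Section 2.4.6.6 adds that, once IRB approval is obtained, "patients discharged within the past 10 weeks will be screened for possible participation". The discharge date is recorded in the enrolment log (2.4.1), but no assessment is scheduled from it.

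**The concern.** As written, the analysis would report a change from a discharge measurement that nobody takes. It would also attach 3-month and 6-month post-discharge labels to values whose true time since discharge depends on how late the patient enrolled. One label would then cover patients at different stages of recovery.

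This matters most for the objective in 2.2, and the stated purpose of the secondary outcomes in 2.4.6.4, of comparing these patients with historical non-COVID PICS patients. Setting a 3-month post-discharge figure from the literature beside values taken at about 5 months in some patients is not a like-for-like comparison.

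The direction of any bias is open. Recovery before enrolment goes unseen, but section 2.1.1 also notes: "Often signs and symptoms of PICS do not manifest until the patient has returned home". In addition, patients are selected for possible symptoms at the telephone screen.

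**Working it through.** **Inputs.** Day 1 = consent; surveys sent Day 1-2; initial visit Day 9-18; survey repeats 10 and 22 weeks after the initial visit; visit repeats 12 and 24 weeks after it (all 2.4.1). Lag from discharge to screening: up to 10 weeks (2.4.6.6). I take the lag at consent as 0, 5 or 10 weeks and read Day 9-18 as the window in which the visit is held.

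**Formula.** Elapsed days = study day - 1, so surveys go out at 0-1 days and the initial visit is at 8-17 days (1.1-2.4 weeks). Then:

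- survey baseline = lag + 0 to 0.1 weeks
- test baseline = lag + 1.1 to 2.4 weeks
- survey repeats = lag + 1.1 to 2.4 + 10 or 22 weeks
- test repeats = lag + 1.1 to 2.4 + 12 or 24 weeks
- months = weeks / 4.348

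**The plan's own time points.** 0, 3 and 6 months after discharge, that is 0, 13.0 and 26.1 weeks.

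**Example, lag 10 weeks.** First survey repeat: 10 + 1.1 + 10 = 21.1 to 10 + 2.4 + 10 = 22.4 weeks, or 4.9-5.2 months. Last test repeat: 10 + 1.1 + 24 = 35.1 to 10 + 2.4 + 24 = 36.4 weeks, or 8.1-8.4 months.

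**Results, in months after discharge:**

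| Assessment | Label in 2.4.6.5 | Lag 0 | Lag 5 weeks | Lag 10 weeks |
|---|---|---|---|---|
| Surveys, baseline | 0 | 0.0 | 1.1-1.2 | 2.3 |
| Tests, baseline | 0 | 0.3-0.6 | 1.4-1.7 | 2.6-2.9 |
| Surveys, first repeat | 3 | 2.6-2.9 | 3.7-4.0 | 4.9-5.2 |
| Tests, first repeat | 3 | 3.0-3.3 | 4.2-4.5 | 5.3-5.6 |
| Surveys, second repeat | 6 | 5.3-5.6 | 6.5-6.8 | 7.6-7.9 |
| Tests, second repeat | 6 | 5.8-6.1 | 6.9-7.2 | 8.1-8.4 |

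At no lag, every follow-up lies within 0.7 month of its label. At a 10-week lag, the 3-month value is 1.9-2.6 months late and the 6-month value 1.6-2.4 months late. Such a patient's baseline sits near the 3-month label and the first repeat nearer the 6-month label.

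Survey times are sending times. The one-week turnaround adds up to 7 days (0.2 month).

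**How many patients might be late.** The documents do not say, so this is an illustration only. Section 2.4.6.6 takes 50% of 29 first-month discharges, 14.5, as about 15 per month, which reproduces. Assume that rate throughout, lags spread evenly over the look-back, and the whole backlog contacted at once:

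- patients in the look-back: 15 x 10 / 4.348 = 34.5
- share with equal uptake over 6 months of enrolment: 34.5 / (34.5 + 90) = 27.7%
- share with equal uptake over 7 months: 34.5 / (34.5 + 105) = 24.7%
- in patients: about 20-22 of the planned 80
- if all of them enrol: 34.5 / 80 = 43%

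Half of these, 12-22% of the 80, would have a lag above 5 weeks.

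**The case against.** The strongest reply is that this is mainly a wording fault in a feasibility study. Whatever the lag, the interval from baseline to repeat is about 11-12 and 23-24 weeks for surveys, and 12 and 24 weeks for tests, so within-patient change is sound. That stands, and it is why the signed-rank test can be kept.

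Second, the plan specifies no time-matched historical test, and most dated figures in its background are at 12 months, with one at 3 months. That also stands: the harm to the historical comparison arises when published figures are matched by time since discharge. The mislabelled change scores remain either way.

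Third, the timing is not wholly detached from discharge. The look-back is meant to start care within 12 weeks of discharge, and a 10-week lag puts the initial visit at 11.1-12.4 weeks. But this bounds entry, not follow-up.

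Fourth, the 10-week limit applies to screening and may concern only the backlog at IRB approval, so late enrollees could be few. Equally, consent could come after screening and so later than 10 weeks. The shares above depend on a rate that 2.4.6.6 itself calls uncertain, and they are not evidence of impact.

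Finally, discharge values might come from chart review or the linked inpatient study. The attachments are not available here, but nothing in the text says that these instruments are collected there.

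**Conclusion.** The concern holds. The Synopsis and 2.4.6.5 describe a baseline that the schedule never measures and follow-up times that it does not anchor to discharge. The displacement is small for patients consented promptly. It grows week for week with the lag, to roughly 2 months or more at a 10-week lag.

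These figures rest on Day 1 being consent, the visit being held on Day 9-18, and surveys dated at sending. A visit held later would lengthen the delay. The share of patients affected and the direction of bias are unknown.

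Only the secondary change scores and time-specific historical comparisons are touched. The point should be corrected before analysis, but it does not threaten the feasibility conclusions.

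**What to change.** - **Relabel.** In 2.4.6.5 and the Synopsis, define change as from enrolment baseline (Day 1-2 surveys; initial virtual visit for Katz and Lawton, sit-to-stand and step test) to the week-10 and week-22 surveys and the week-12 and week-24 visits. Keep the signed-rank test on that basis.
- **Report actual timing.** Derive days since discharge for every assessment from the logged discharge date. Give the median, interquartile range and range at each time point.
- **Adjust.** Add the discharge-to-baseline lag as a covariate in the planned ANCOVA, whose covariates are listed only as examples.
- **Restrict the historical comparison.** Set a comparison with a published 3- or 6-month post-discharge figure only against assessments whose actual time since discharge falls in a window stated before the data are examined.
- **Optional.** A mixed model in time since discharge as a sensitivity analysis.

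The cost is wording in two places, one derived variable and one covariate, with no new visits or data. The real price is that fewer patients will enter the time-matched historical comparison.

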### 2.1 Background and Significance

#### *Background:*

Coronavirus disease 2019 (COVID-19) is a highly contagious virus transmitted via respiratory secretions and was established as a pandemic on March 11, 2020. The severity of the disease ranges from asymptomatic/mild (81%), to severe requiring oxygen (14%) and critical (5%) which requires intensive care unit (ICU) admission, ventilation and life support. Two-thirds of these severe cases will develop the most severe manifestation of the disease, acute respiratory distress syndrome (ARDS). Various epidemiologic reports show that the greatest mortality and morbidity risks concern frail and vulnerable people, in particular the elderly, and patients who suffer from multiple comorbidities or chronic diseases (mainly hypertension, diabetes, cardiovascular disease, chronic, respiratory disease, immune compromised status). Patients requiring a stay in the ICU often have a considerably longer length of stay (LOS) than the typical ICU patient. At Barnes-Jewish Hospital (BJH) the typical LOS for an intubated ICU patient with COVID-19 disease is 10-12 days, whereas a non-COVID-19 medical ICU patient is 3-4 days. Thus far, the greatest attention has been paid to strategies to control contagion diffusion and life-saving measures for these critically ill infected patients. It is now time to focus on the inevitable long-term consequences of surviving COVID-19 disease. This feasibility study will provide information not only regarding the long-term sequelae of COVID-19 disease, but also how to structure future care with a primary emphasis on telehealth, both of which may be important if society is faced with another highly contagious disease.

The patients that survive will likely suffer from secondary physical, cognitive and mental impairments due to their prolonged stay in the ICU. Together, these components comprise the Post Intensive Care Syndrome (PICS). PICS purportedly affects 50 – 70% of ICU survivors which may develop during their stay or after discharge and it is estimated one-third of these survivors will die within a year. Post COVID-19 patients may be at increased risk of PICS due to a prolonged period of respiratory distress and immobility along with the potential of lung fibrosis and cardiovascular

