#### **2.5.2 Premature Discontinuation**

Subjects will be withdrawn if the investigator decides that discontinuation is in the best interest of the subject, inactivity by the subject or the subject requests withdrawal from the study.

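### Symptom change is tested only on complete pairs, with no missing-data plan or confidence interval, so health-related loss would bias the reported recovery in a direction that cannot be known in advance

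*Combined protocol and SAP*

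**What the plan says.** Section 2.4.6.5 (Statistical Methods), repeated in the Synopsis, names one method for change on every instrument. Changes "from hospital discharge to 3- and 6-month post discharge" "will be estimated using the Wilcoxon Signed Rank Test (non-parametric alternative to t-test"), and are then compared across patient characteristics by ANOVA or ANCOVA. The same section promises medians with interquartile ranges, or means with standard deviations, for continuous variables. It gives no longitudinal model, imputation, attrition comparison, sensitivity analysis or confidence interval.

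Section 2.4.1 (Study Procedures) sends surveys after consent and again at weeks 10 and 22 after the initial visit. I take these as the three assessments. A patient who does not finish them within seven days and has not responded to calls is "considered an enrollment fail (start of study) or withdrawal from study (repeat surveys), document on enrollment log". For the repeat rounds this is timed at "Week 11 and Week 23 post initial visit". Section 2.5.2 also withdraws patients for "inactivity by the subject or the subject requests withdrawal from the study". The Katz and Lawton scales, the sit-to-stand test and the step test are done at the virtual visit only with patients who are willing and able. On mortality, the Background says that "it is estimated one-third of these survivors will die within a year".

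**The concern.** A signed-rank test needs a first and a later score from the same patient. The plan never uses the term complete pairs, but with this test and no missing-data rule it is the natural reading. A patient withdrawn at week 11 has neither a 3-month nor a 6-month score, so the first score is unused in every change analysis, including the ANOVA and ANCOVA comparisons. A patient lost between weeks 11 and 23 contributes to the 3-month change only.

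The protocol itself gives reasons why loss may be related to health: death, non-response in people recovering from critical illness, and performance tests that depend on ability. If so, the average change among completers is not the average change among those enrolled. The word estimated also promises more than the test delivers. It yields a p-value, and no interval for the size of change is planned. Symptoms are to be set beside published non-COVID cohorts, and that needs a size with its uncertainty.

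**Working it through.** **Figures in the plan.** The planned number is 80. The documents give no dropout rate, score SD, correlation, expected change or significance level, so there is no figure to reproduce and the inputs below are assumptions.

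**Assumed inputs.** Score SD 10, higher = better; correlation between first and later score ρ = 0.6; true mean change +5. Loss is 10%, 20% or 40%, which leaves 72, 64 or 48 pairs of 80. Loss follows a logistic model with odds of loss of 1.6, 2.2 or 3.3 per SD worse.

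**Formulas.** Let d be the completers' mean minus the all-patient mean on the score that drives loss, found numerically from the logistic model.

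- Loss driven by the first score: complete-pair bias = (ρ − 1)d = −0.4d.
- Loss driven by the follow-up score: complete-pair bias = (1 − ρ)d = +0.4d.
- Likelihood estimate using all first scores (the two-visit equivalent of a mixed model): bias is 0 when loss is driven by the first score. When it is driven by the follow-up score, bias = d(1 − bρ), where b is the slope of follow-up on first score among completers.
- Random loss: d = 0, so no bias for either method.

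**Results (true change 5).**

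| Loss | Odds per SD | d | Complete pairs, first-score-driven loss | Shortfall | Complete pairs, follow-up-driven loss | b | All-scores estimate, follow-up-driven loss |
|---|---|---|---|---|---|---|---|
| 10% | 1.6 | 0.46 | 4.8 | 4% | 5.2 | 0.59 | 5.3 |
| 10% | 2.2 | 0.74 | 4.7 | 6% | 5.3 | 0.58 | 5.5 |
| 10% | 3.3 | 1.03 | 4.6 | 8% | 5.4 | 0.56 | 5.7 |
| 20% | 1.6 | 0.90 | 4.6 | 7% | 5.4 | 0.59 | 5.6 |
| 20% | 2.2 | 1.43 | 4.4 | 11% | 5.6 | 0.57 | 5.9 |
| 20% | 3.3 | 1.96 | 4.2 | 16% | 5.8 | 0.54 | 6.3 |
| 40% | 1.6 | 1.78 | 4.3 | 14% | 5.7 | 0.58 | 6.2 |
| 40% | 2.2 | 2.77 | 3.9 | 22% | 6.1 | 0.55 | 6.9 |
| 40% | 3.3 | 3.74 | 3.5 | 30% | 6.5 | 0.52 | 7.6 |

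Worked row (40%, odds 2.2): 0.4 × 2.77 = 1.11, so 5 − 1.11 = 3.9 or 5 + 1.11 = 6.1. For the all-scores estimate, 2.77 × (1 − 0.55 × 0.6) = 1.86, giving 6.9.

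Simulated trials of 80 agree. At 40% first-score-driven loss, the complete-pair Hodges-Lehmann estimate averages about 4.3 / 3.9 / 3.5 and the all-scores estimate about 5.0 throughout. Their standard errors are similar (1.31–1.37 and 1.28–1.31).

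**Size against sampling error.** The SD of change is 10√(2 × 0.4) = 8.94. The standard error is 8.94/√72 = 1.05, 8.94/√64 = 1.12 or 8.94/√48 = 1.29. Complete-pair bias runs from 0.18/1.05 = 0.2 standard errors (10% loss, weakest dependence) to 1.50/1.29 = 1.2 (40% loss, strongest). At ρ = 0.8 the bias halves, because 1 − ρ falls from 0.4 to 0.2.

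**False positives.** This check used N = 80, no true change, ρ = 0.5 and a probit loss model with slope 1 per SD. That dependence is stronger than above: roughly exp(1.6) ≈ 5 in odds. At 20 / 35 / 50% loss, the nominal 5% Wilcoxon test rejects 17 / 30 / 41% of the time when loss follows the follow-up score, almost always towards recovery. It rejects 17 / 31 / 43% when loss follows the first score, almost always towards worsening. Under random loss it rejects 4–5%.

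**Deaths.** One-third within a year, at a constant hazard (assumed), is 1 − (2/3)^0.25 = 10% by 3 months and 1 − (2/3)^0.5 = 18% by 6 months.

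**The case against.** The study is an observational feasibility study. Its primary outcomes are adherence, attendance, punctuality, questionnaire completion and acceptability, and no stated decision turns on the size of within-patient change. A signed-rank test is defensible for ordinal or bounded scores at this sample size. The plan also works to keep patients: a reminder at five days, a call offering telephone completion at seven, and contact every two weeks after the first and second team visits. A missed online survey alone does not mean withdrawal. All of this stands. It makes the point one of good practice on secondary outcomes.

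A reader might infer four stronger things that the documents do not support.

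- **The plan understates recovery by 15–30%.** That holds only for 40% loss driven by baseline severity. The documents state no loss rate, and the sign reverses when loss follows poor recovery.
- **Patients lost by week 11 contribute nothing.** They still enter the baseline descriptives and the attendance and completion outcomes.
- **No size of change will be reported.** The general promise of medians or means with a spread can cover change scores. What is missing is an interval.
- **The 3- and 6-month results describe progressively healthier groups, giving a false trend.** This is possible, but the documents give nothing to establish it, and the calculations here use a single follow-up.

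The other serious objection is to the remedy. A mixed model is unbiased in the first-score-driven case by construction. In the follow-up-driven case it is further from the truth than complete pairs (6.9 against 6.1 in the worked row). That stands, and the model should not be adopted alone.

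**Conclusion.** The concern holds in a limited form. The change analyses rest on complete pairs, withdrawal for non-response removes patients from them, and the plan has no missing-data method, no handling of deaths and no confidence interval for change.

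Bias arises only if loss is related to health. Under the assumptions above, loss by baseline severity understates recovery by about 4–16% at 10–20% loss and about 15–30% at 40% loss. Loss by follow-up status overstates it by the same amounts. Random loss causes none, and neither does baseline-driven loss if change is unrelated to baseline. The sizes depend on assumed loss, correlation and strength of dependence, so they show what could happen and do not predict this study's result. The change is worth making before analysis, but it does not threaten the primary feasibility conclusions.

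**What to change.** Amend section 2.4.6.5 and the Synopsis as follows.

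1. For approximately continuous scores (such as PROMIS-29 T-scores, MoCA and the timed tests), fit a mixed model for repeated measures to all available assessments from every patient with a first score. Use categorical visit and unstructured covariance. Enter the first score as an outcome rather than a covariate, so that patients with only that score stay in. Report mean change at 3 and 6 months with 95% confidence intervals.
2. Keep the complete-pair Wilcoxon test as sensitivity, with a Hodges-Lehmann estimate and confidence interval. Make it the main analysis for strongly bounded scores such as Katz.
3. Compare baseline characteristics of completers and non-completers.
4. Tabulate deaths separately, and state that change is read among those alive.
5. Add a missing-not-at-random sensitivity analysis, for example one that shifts the unseen scores by a range of deltas. The mixed model removes bias only if loss depends on observed scores.

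The cost is SAP wording and a little more programming, with no new data. The model brings missing-at-random and approximate-normality assumptions, which is why items 2 and 5 belong with it.
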